##### Confirmation of Eligibility

All potential registry participants shall be confirmed as meeting eligibility requirements, as described in labeled indications for use and contraindications.

##### Informed Consent

All patients seeking to participate in the registry, and whose eligibility has been confirmed by the Investigator, will be required to sign Sponsor-provided Informed Consent prior to enrollment.

##### Demographic Information

Date of birth, gender, height, weight, and smoking history will be collected.

Establishment of Self-Defined Functional Objective

### **3.5.2 Intra-Operative Assessment**

Perioperative metrics will be collected and documented on the Treatment Case Report Form (Appendix B) at the time of treatment, including:

- Device size(s)
- Device lot number(s)
- Surgical level(s) treated
- Type of anesthesia
- Duration of surgery (min.), measured from start of anesthesia administration to completion of skin closure
- Estimated blood loss (cc)
- Time to discharge (hrs.), measured from completion of skin closure to discharge from treating facility

In addition, any intra-operative complications/serious adverse events deemed by the Investigator to be definitely procedure- or device-related will be documented, as described in §4.

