**Postmarket Registry for Evaluation of the Superion® Spacer**

**[PRESS Registry]**

**Protocol No. 16-VIIS-01**

**PROTOCOL SYNOPSIS**

Title	Postmarket Registry for Evaluation of the Superion® Spacer
Short Title	PRESS Registry
Protocol Number	16-VIIS-01
Sponsor	Vertiflex® Inc. [name]
Registry Treatment	Superion® Indirect Decompression System (IDS)
Control Treatment	None
Registry Design	Prospective, single arm, multi-center
Registry Objective	The purpose of this postmarket surveillance registry is to gather evidence documenting the performance and clinical outcomes associated with treatment of moderate degenerative lumbar spinal stenosis using the Superion® Indirect Decompression System (IDS) .
Registry Population	Patients $\geq$ 45 years of age suffering from symptoms of neurogenic intermittent claudication secondary to a confirmed diagnosis of moderate degenerative lumbar spinal stenosis at one or two contiguous levels from L1 to L5.
Number of Subjects	A minimum of one hundred (100) patients will be enrolled in the registry.
Number of Sites	A minimum of twenty (20) sites will participate.
Registry Enrollment	Approximately 12 months for a minimum of 100 patients.
Registry Duration	Patients included in the clinical registry will return for follow-up visits at 3 weeks, and 6 and 12 months post-treatment to collect data for the primary evaluation. Registry duration is approximately 24 months based upon 12 months' enrollment plus 12 month follow-up for 100 patients. Sponsor reserves the right to enroll additional patients.
Endpoints	

VertiFlex® Patient Satisfaction Survey: A score of <math>\geq</math>3 in each questionnaire component is considered clinically significant;

Visual Analogue Scale (VAS): An improvement in back and leg pain of 20 mm (on a 100 mm scale) vs. baseline is considered clinically significant.

Achievement of Self-Defined Functional Objective. A score of <math>\geq</math>3 is considered evidence of significant improvement in function.

Other Data Collected	

Reports of serious procedure- or device-related adverse events;

Intraoperative metrics including estimated blood loss, operative time, type of anesthesia, and time to discharge.

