## 2 PRODUCT DESCRIPTION

The Superion® Indirect Decompression System (IDS) (Superion® implant) is a spinal implant designed to treat symptoms of neurogenic intermittent claudication secondary to moderate degenerative lumbar spinal stenosis, and is implanted by minimally-invasive methods through a cannula with patient under general or local anesthesia. The implant provides indirect decompression of spinal nerves, and functions as a spinal extension-blocker to prevent compression of neural elements in extension. The device was approved by the U.S. Food and Drug Administration (FDA) for commercialization in the U.S. via PreMarket Approval (PMA) on May 20, 2015.

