**Figure 1: Superion® Indirect Decompression System (IDS) *in situ***

**Lateral View**

**A/P View**

For a complete Summary of Safety and Effectiveness Data (SSED) derived from the clinical trial supporting FDA approval of the Superion® PMA, please refer to the SSED posted on the FDA website at [http://www.accessdata.fda.gov/cdrh\\_docs/pdf14/P140004b.pdf](http://www.accessdata.fda.gov/cdrh_docs/pdf14/P140004b.pdf).

The device may be implanted under general or local (e.g., conscious sedation) anesthesia. A percutaneous or mini-open approach is used for placement of a cannula via sequential dilation. A sizing tool is employed to determine the proper device size, and the Superion® implant is then inserted through the cannula and deployed under fluoroscopic guidance between spinous processes at the level to be treated. The implant serves thereafter to maintain distraction between the spinous processes while preserving motion. This maintains the intervertebral space and prevents narrowing of the canal by limiting extension at that level. Where a second, contiguous level is also symptomatic, the same procedure is used to place a Superion® implant at that level.

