## **3.2 Registry Endpoints**

Registry endpoints will include the following outcomes reflective of clinical effectiveness:

- Vertiflex® Patient Satisfaction Survey: A score of  $\geq 3$  in each questionnaire component will be deemed a clinically meaningful outcome.
- Visual Analogue Scale (VAS), Back and Leg Pain: An improvement of 20 mm (on a 100 mm scale) from baseline is considered a clinically meaningful outcome.
- Achievement of Self-Defined Functional Objective. A score of  $\geq 3$  is considered evidence of significant improvement in function.

In addition, other information to be collected will include:

- Reports of Serious Adverse Events (SAEs) determined by the Investigator to be definitely procedure- or device-related.

Perioperative information that will be collected includes:

- Type of anesthesia
- Operative time (min.)
- Estimated blood loss (cc)
- Time to discharge (hrs.)

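### Does timing the duration of surgery from the start of anesthesia make the registry's operative time misleading?

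*Protocol*

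**What the plan says.** The synopsis, under other data collected, lists "Intraoperative metrics including estimated blood loss, operative time, type of anesthesia, and time to discharge". Section 3.2 gives four perioperative items, among them one beginning "Operative time (min" and another, "Type of anesthesia". Neither place says when the operative clock starts or stops.

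Section 3.5.2 supplies the measurement rules for the Treatment Case Report Form. It does not use the term operative time. The matching entry reads "Duration of surgery (min.), measured from start of anesthesia administration to completion of skin closure". The entry for discharge in the same list reads "Time to discharge (hrs.), measured from completion of skin closure to discharge from treating facility".

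On anesthesia, section 2 says the device "is implanted by minimally-invasive methods through a cannula with patient under general or local anesthesia", and section 2.1 says "The device may be implanted under general or local (e.g., conscious sedation) anesthesia".

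**The concern.** Two things look wrong. First, one quantity carries two names, and the places that call it operative time do not define it. Second, the definition in section 3.5.2 mixes two kinds of event: the clock starts at an anesthetic event and stops at a surgical one. The result is neither incision-to-closure time nor full anesthesia time.

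Two consequences would follow if this mattered. A reader who sees a mean operative time could take it as surgical time and set it beside incision-to-closure figures from elsewhere, where it would look too long. And if the lead time before incision differs between general and local anesthesia, a pooled summary would depend partly on the mix of anesthesia types in the registry and not only on the procedure.

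This is also a data-collection rule. If incision time is not written down on the day, no later analysis can separate the two parts.

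**Working it through.** The protocol states no operative-time figure, so there is nothing to reproduce. The check is a comparison of the wording, followed by one identity.

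**Same item or not.** The perioperative content of the three lists, side by side:

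| Place | Anesthesia | Time in theatre | Blood loss | Discharge |
|---|---|---|---|---|
| Synopsis | listed | operative time, no end points | listed | listed, no end points |
| Section 3.2 | listed | operative time, no end points | listed | listed, no end points |
| Section 3.5.2 | listed | duration of surgery, both end points given | listed | listed, both end points given |

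Each list has exactly one candidate for the time in theatre. Equating the two names is an inference, but no other item fits. Time to discharge follows the same pattern: it is bare in the synopsis and section 3.2 and defined in section 3.5.2. The two earlier places are summary lists, and the procedures section holds the definitions.

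**What is recorded.** Let L be the minutes from the start of anesthesia to incision and S the minutes from incision to the end of closure. Then

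- recorded value = L + S
- excess over surgical time, as a proportion = L / S
- difference between anesthesia types for the same surgery = L(general) − L(local), whatever S is.

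**Size.** The protocol gives neither L nor S. Purely as an assumption, take S = 60 min and L between 5 and 30 min: the excess is 5/60 = 8% to 30/60 = 50%. If lead times are equal under the two types of anesthesia, the difference by type is 0. With assumed lead times of 15 to 30 min for general and 5 to 10 min for local anesthesia, it is 15 − 10 = 5 min up to 30 − 5 = 25 min. These numbers show only that the two intervals are different quantities. They do not show that the protocol chose the wrong one.

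**Does anything depend on it?**

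- The three endpoints are the satisfaction survey, the pain scales and the self-defined functional objective. The time in theatre is not among them.
- There is no control treatment, and the protocol sets no threshold or comparison for this item.
- The only size statement is "A minimum of one hundred (100) patients will be enrolled in the registry"; it is not derived from this item or from any variance.

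**Are the clocks coherent?** The duration clock stops at the end of skin closure and the discharge clock starts there. The two intervals neither overlap nor leave a gap.

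**The case for a change.** The strongest case for a change is that the label promises surgery while the clock counts something else, that this is fixed at data collection and so cannot be left to an analysis plan, and that relabelling costs almost nothing. A registry meant to document device performance, with only four perioperative items in section 3.2, ought to make each of them unmistakable.

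Part of this stands. The two names do differ, the recorded value does include time before incision, and that time may vary with anesthesia type. Recording the type allows a summary within type but does not by itself separate L from S.

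The rest is weaker. That surgical time cannot be recovered is not established: the list in section 3.5.2 is introduced as inclusive rather than exhaustive, and the Treatment Case Report Form is not at hand, so it may or may not capture incision time. Preferring incision-to-closure is a choice between two legitimate intervals, and nothing in the protocol says the metric must isolate surgical time. The misreading also requires a reader to ignore a definition that the protocol states. Whether to summarise by anesthesia type is a reporting decision that normally belongs in the analysis plan, and the data for it are already collected.

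**Conclusion.** The observation is accurate, but it does not call for a change to the plan. Section 3.5.2 gives one explicit, uniformly applicable rule that does not conflict with anything else in the protocol. Anesthesia type is recorded, so any dependence on the anesthesia mix can be shown in the report without altering data collection.

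The size of the pre-incision component is unknown, because the protocol gives no minutes. Even a large value would leave every endpoint result unchanged, since the item is descriptive and has no threshold, control or planned comparison. The remaining inconsistency, two near-synonyms for one item, is clerical; whoever writes the report can state the end points of the interval beside the figure.

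This conclusion rests on two assumptions: that operative time and duration of surgery are the same item, which the parallel lists support, and that the case report form does not contradict the section 3.5.2 rule, which cannot be checked here.

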### **3.5.3 Post-Operative Follow-Up Assessments**

At each follow-up visit, i.e., at 3 weeks ( $\pm 2$  weeks), 6 months ( $\pm 2$  months), and 12 months ( $\pm 2$  months) post-treatment, the following information will be collected and documented on the Follow-Up Visit Case Report Form (Appendix B):

- Patient identification number and initials, and date of follow-up visit and follow-up interval (e.g., 3 weeks, 6 or 12 months, etc.) will be recorded by the Investigator and/or his/her authorized clinical research staff.
- Patients will complete a Vertiflex® Patient Satisfaction Survey. A score of  $\geq 3$  in each questionnaire component will be deemed a clinically meaningful outcome.
- Patients will complete a Visual Analogue Scale (VAS) for each leg, and for back pain. An improvement of 20 mm (on a 100 mm scale) from baseline is considered a clinically meaningful outcome.
- Patients will indicate the extent to which they have achieved their Self-Defined Functional Objective, on a 1 to 5 scale, with 1 indicating no progress at all, and 5 indicating complete achievement.

In addition, the Investigator and/or his/her authorized clinical research staff will collect and document:

- Reports of any Serious Adverse Events (SAEs) occurring since the last visit, and determined by the Investigator to be definitely procedure- or device-related.

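### Does the 20 mm VAS criterion need rewording because it does not say whether back and leg are judged together, or which leg counts?

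*Protocol*

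**What the plan says.** The VAS criterion appears three times in the protocol.

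- **Synopsis, Endpoints:** "An improvement in back and leg pain of 20 mm (on a 100 mm scale) vs. baseline is considered clinically significant".
- **Section 3.2:** "Visual Analogue Scale (VAS), Back and Leg Pain: An improvement of 20 mm (on a 100 mm scale) from baseline", which is then called clinically meaningful.
- **Section 3.5.3:** "Patients will complete a Visual Analogue Scale (VAS) for each leg, and for back pain". The same 20 mm threshold follows in the next sentence, stated once.

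The patient satisfaction survey also has several parts. Its threshold of at least 3 carries a component phrase, "in each questionnaire component will be deemed a clinically meaningful outcome" (section 3.2), and the VAS bullet has no such phrase. The synopsis describes the follow-up visits as "post-treatment to collect data for the primary evaluation". It does not single out one of the three listed endpoints as primary.

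The design is single-arm with no control and a minimum of 100 patients. The protocol gives no derivation of that number and no target response rate.

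**The concern.** The synopsis speaks of leg pain in the singular and joins it to back pain in one sentence. A reader could take that as a joint requirement, with both back and leg having to improve by 20 mm. Sections 3.2 and 3.5.3 can be read as separate criteria. Section 3.5.3 also yields two leg scores, and nothing says whether leg response means the worse leg, either leg, both legs or their average.

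If the criterion is reported as a percentage of patients, these readings give different percentages from the same data. With no control arm, a reported rate stands on its own. Leaving the rule open until the data are in could let the more favourable figure be chosen. The satisfaction-survey wording seems to show that the authors knew how to state a component rule and did not do so for the VAS.

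**Working it through.** **There is no plan figure to reproduce.** The protocol links no rate, power, alpha or standard deviation to the VAS criterion. The check is therefore a reading of the text, followed by an illustration on assumed inputs.

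**1. Do the passages conflict?**

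| Place | What it contributes |
|---|---|
| Synopsis | Names the two pain sites and the 20 mm threshold on a 100 mm scale |
| 3.2 | Uses the same two sites as a label, with the same threshold |
| 3.5.3 | Says how they are recorded (two legs and back), then the same threshold |

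The threshold is tied to a 100 mm scale, so it is a distance on a single scale. No summed or averaged score is defined to which it could otherwise apply. None of the three places speaks of a composite or says that both sites must respond. The per-scale reading fits all three, and the joint reading is possible only from the synopsis sentence taken alone.

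**2. Does the satisfaction survey show a deliberate contrast?** Not clearly. The phrase "in each questionnaire component is considered clinically significant" can mean that every component must reach 3, or that 3 is the threshold for each component taken singly. It carries the same ambiguity, so it does not show that the protocol settles one endpoint and neglects the next.

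**3. How far could the readings differ for one patient?** Take the left leg from 60 to 30, the right leg from 5 to 5, and the back from 50 to 40.

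- Worse leg: 60 − 30 = 30 mm, met.
- Mean of legs: 32.5 − 17.5 = 15 mm, not met.
- Back: 50 − 40 = 10 mm, not met.
- Back and leg jointly: not met.

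**4. How far could the rates differ?** Let p_L and p_B be the leg and back response rates. The joint rate lies between max(0, p_L + p_B − 1) and min(p_L, p_B). With both assumed to be 70%, the bounds are 0.70 + 0.70 − 1 = 40% and 70%. Bivariate normal probabilities give:

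| Assumed rate on each | Joint rate, correlation 0.3 | 0.5 | 0.7 |
|---|---|---|---|
| 60% | 41% | 44% | 48% |
| 70% | 53% | 56% | 59% |

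At 70% the joint rate is 11 to 17 points lower than the separate one.

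**5. What is the right yardstick for that gap?** The 95% half-width of a single proportion at 70% and n = 100 is 1.96 × √(0.7 × 0.3 / 100) = 9.0 points. It does not measure this gap, because both readings are applied to the same patients. The gap is the share who respond on one site but not on the other. At 70% and correlation 0.5 that share is 70% − 56% = 14%, and its own half-width is 1.96 × √(0.14 × 0.86 / 100) = 6.8 points. The two readings are simply different quantities, and setting their difference against sampling error does not show a fault in the plan.

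**6. Is there one correct leg rule that the protocol missed?** No. Suppose the leg worse at baseline is chosen, the legs are truly equal, and nothing changes. The expected spurious fall is then the measurement SD divided by √π: 8 / 1.772 = 4.5 mm, or 12 / 1.772 = 6.8 mm (both SDs assumed). Taking the higher leg score at each visit avoids this bias in the mean. In a simulation on assumed inputs, the two rules gave response rates of 70–73% and 64–67%, 3 to 9 points apart. The choice is a trade-off for the analyst.

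**The case for a change.** The strongest case for a change is that the protocol itself chose to write a responder threshold in three places, and that the leg part cannot be applied as written without a further decision. The fix would be about two lines, and fixing the rule before the data are seen removes a choice. In a single-arm registry, where VAS is one of three listed endpoints, that has some value.

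Part of this stands. No visible text names the leg score, and no sentence says outright that back and leg are judged separately. The closed-form arithmetic for the joint rate is also correct.

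The step from there to a defect does not stand. The passages are compatible. The word primary in the synopsis describes what the visits collect and does not make the VAS a primary endpoint. The harm is conditional on a responder rate being reported, and the protocol commits to no such rate, denominator or target. Section 3.5.3 records each follow-up score on its own scale, so the text does not force an irreversible choice at collection. For baseline this is inferred from the reference to change from baseline, because the visible part of section 3.5.1 does not describe the VAS and text may be missing there.

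**Conclusion.** The concern does not call for a change. What is missing is a derivation detail: which leg score is used, and an explicit statement that the threshold applies scale by scale. A statistical analysis plan commonly settles this, and only the protocol was available. An analyst reading sections 3.2 and 3.5.3 together would sensibly report back and leg separately and state a leg rule.

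The 11 to 17 point gap between the joint and separate readings is real arithmetic, but it rests on an assumed 70% rate and assumed correlations of 0.3 to 0.7. The protocol supplies neither, so the true size is unknown. No hypothesis, success criterion, sample size or stated figure in the protocol depends on the answer.

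The conclusion assumes that the leg score and the per-scale reading are settled before the outcome data are analysed. If the analysis plan were silent on both, a single clarifying sentence there would be enough.

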## 4 SERIOUS ADVERSE EVENTS (SAEs)

All Serious Adverse Events (SAEs) deemed by the Investigator to be **definitely procedure- or device-related** must be documented on the SAE Case Report Form (Appendix B).

### 4.1 Serious Adverse Events

An adverse event is regarded as a **Serious Adverse Event (SAE)** if the injury or illness:

- A) Results in death
- B) Is life-threatening,
- C) Results in or prolongs hospitalization
- D) Results in permanent impairment of a body function or permanent damage to a body structure, or
- E) Necessitates medical or surgical intervention to preclude permanent impairment of a body function or permanent damage to a body structure.

The Vertiflex® Clinical Research group must be notified of all **Serious Procedure- or Device-Related Adverse Events** within 24 hours at:

Vertiflex®, Inc., Clinical Research  
[name] USA  
[contact]  
[contact]  
[[contact]](mailto:[contact])

## 5 TERMINATION OF PARTICIPATION

Patients may voluntarily withdraw from the registry at any time for any reason. The Investigator(s) may elect to withdraw a subject from the registry at any time due to lack of compliance or for any reason unrelated to the registry treatment if such a decision is in the patient's best medical interest.

## 6 DEVICE EXPLANT AND RETRIEVAL

In the event of a device removal, the device and the Investigator's written explanation of the event will be sent to Vertiflex® following instructions from Vertiflex®.

## 7 INVESTIGATOR RESPONSIBILITIES

Investigators will be deemed responsible for the following:

- This registry must have initial and continuing approval (at least annually) from an Institutional Review Board (IRB) responsible for approving clinical studies.
- Acquisition of signed Informed Consent from each patient before performing any registry-related activities.
- Conduct of the registry in conformance with this protocol, and with Good Clinical Practices.

## **8      Vertiflex® OBLIGATIONS**

### **8.1    Investigator(s) Training**

Vertiflex® will provide appropriate training to each Investigator that includes didactic and hands-on elements, e.g., cadaver lab, sawbones model. Training will include surgical procedures in accordance with the Superion® Surgical Technique Manual, selection of appropriate implant sizes, instrumentation for implantation, indications for use of the device, contraindications, and management of complications. Vertiflex® will also provide appropriate training to the operating room staff at each investigational site, where applicable.

